8.6. PREGNANCY AND IN UTERO DRUG EXPOSURE

Subjects who have been exposed to study treatment and who become pregnant during the treatment period will be immediately withdrawn from treatment. Pregnancies that have been exposed to study treatment and/or started before the Week 64 visit or - **in case of early withdrawal** - up to 4 weeks after treatment discontinuation will be followed up for pregnancy and neonatal outcomes at birth. Any pregnancy must be reported with the Pregnancy Surveillance Form (PSF; see below).

Initial reporting of pregnancies:

Subjects who become pregnant during the study treatment period will be immediately withdrawn from the IMP treatment.

The Investigator must notify the Sponsor in an expedited manner (same as for SAE reporting) of any pregnancy occurring during the above-mentioned period, by completing the **PSF-part I**.

This form should be sent to ObsEva's Representative for Pharmacovigilance as per the same procedures and timelines described for expedited AE reporting in section 8.3.2. This form should be accompanied, as needed, by copies of the eCRF Medical History, Previous and Concomitant Therapy and the Exit Form.

Follow-up of pregnancies:

The Investigator must actively follow-up, document and report to ObsEva's Representative for Pharmacovigilance the progress by **tri-monthly updates up to the final outcome of the pregnancy** using the **Pregnancy Surveillance Form** – **Part II**: (Course of Pregnancy; PSF-II). If the subject can no longer be reached (lost to follow-up), documentation of the non-response/contact with two phone calls and a letter (certified with return receipt) are required.

Pregnancy outcomes are not recorded in the eCRF unless considered AEs.

Pregnancy outcomes must be reported to ObsEva's Representative for Pharmacovigilance by completing the **Pregnancy Surveillance Form – Part III**: (Course and Outcome of Pregnancy; PSF-part III). Timelines vary according to the nature of the pregnancy outcome:

- For normal outcomes, ObsEva's Representative for Pharmacovigilance should be notified within 45 days of birth/delivery.
- For abnormal outcomes, the fully completed form must be sent to ObsEva's Representative for Pharmacovigilance according to the same procedures and timelines described for expedited AE reporting in section 8.3.2 (within 24 hours of awareness of this outcome). An SAE Report form must be completed when the subject sustains an event while PSF-part III must be completed when the child/fetus sustains an event. Abnormal outcomes are defined as:
 - Abnormality of the baby (birth defect): in this case, an SAE form for the child should be completed in addition to the PSF-III.
 - Abnormality for the pregnancy (spontaneous abortion, stillbirth) or abnormality for the birth itself which could fulfill criteria of SAEs (e.g. prolongation of hospitalization due to caesarean section complications): in this case please complete an SAE form for the mother in addition to the PSF-III.

9. DATA ANALYSIS AND STATISTICS

9.1. TEST OF HYPOTHESES

The primary endpoint of the study will be assessed as the percentage of subjects with reduced menstrual blood loss at 24 weeks of treatment (last 28 days prior to the Week 24 visit), defined as menstrual blood loss \leq 80 mL and \geq 50% reduction from baseline. The primary analysis of the primary endpoint will be conducted by testing the null hypothesis of no treatment effect for each OBE2109 group vs placebo against the two-sided alternative:

Null hypothesis (H0): "There is no difference in the percentage of subjects meeting the primary endpoint for OBE2109 vs placebo".

H0: p (OBE2109) = p (placebo)

Alternative hypothesis (H1): "There is a difference in the percentage of subjects meeting the primary endpoint for OBE2109 vs placebo".

H1: $p(OBE2109) \neq p(placebo)$

Where p is the percentage of subjects with reduced menstrual blood loss at 24 weeks of treatment.

9.2. SAMPLE SIZE

The planned sample of 500 subjects is based primarily on the requirements for the total number of exposed subjects required for drug registration. In terms of the primary efficacy endpoint, under the assumption of a 30% response rate in placebo and 70% response rate in an active arm based on data from a similar study/compound (AbbVie 2016), a conservative 64 subjects per treatment group are

required for at least 90% power for rejecting all of the OBE2109 group vs placebo group comparisons, each tested separately using a Bonferroni corrected type I error of 0.0125 (0.05 divided by 4). An increased sample size beyond 64 subjects per arm will help ensure success over the overall clinical program given that superior efficacy has to be demonstrated in two independent studies and for potentially additional secondary endpoints, as well as adequately assess the safety endpoints for example the bone mineral density loss.

9.3. RANDOMIZATION

A computer - generated random list using the stratification method and created by FlexRandomizer software (Cytel Inc., Boston, MA, USA) will be used for randomization. Allocation of treatment will be performed via a centralized IWRS system. Subjects will be randomized to one of five treatment groups in a 1:1:1:1:1 ratio for OBE2109 placebo, OBE2109 100 mg without add-back, 100 mg with add-back, OBE2109 200 mg without add-back and OBE2109 200 mg with add-back, stratified by race in order to ensure an equal representation of black women between treatment groups.

Subjects will be randomized into blocks of a pre-determined length.

At Week 24 visit, half of the subjects from the Placebo OBE2109 + Placebo E2/NETA arm will be switched to OBE2109 200 mg with add-back (E2 1 mg/NETA 0.5 mg) while the other half will remain on placebo. This allocation will be determined as part of the randomization at Randomization Call (R) and treatment will be continued up to Week 52.

9.4. ANALYSIS SETS

The following data sets will be used for the statistical analysis:

- 1. **Safety Set:** All randomized subjects who received at least one dose of double-blind study drug irrespective of the treatment received. Subjects will be analyzed according to treatment received.
- 2. **Full Analysis Set (FAS):** All randomized subjects who received at least one dose of doubleblind study drug irrespective of the treatment received. Subjects will be analyzed according to randomized treatment.
- 3. Week 24 Per Protocol (PP) set: All subjects in the FAS excluding those identified as major protocol violators up to Week 24.
- 4. Week 52 Per Protocol (PP) set: All subjects in the FAS excluding those identified as major protocol violators up to Week 52.

As per the analysis set defined above, randomized subjects who withdraw from the study prior to treatment will not be included for the statistical analyses. As this is a double-blind study with a single centralized randomization list (stratified only by race) the decision of whether or not to begin treatment could not be influenced by knowledge of the assigned treatment.

9.5. DATA ANALYSIS

More details of the proposed statistical analysis will be documented in the Statistical Analysis Plan (SAP), which will be finalized prior to the database lock and unblinding of the Week 24 data.
Categorical data will be presented using counts and percentages of subjects, while continuous variables will be presented using the mean, standard deviation, median, 1st and 3rd quartiles, minimum, maximum, and number observations. Raw data will be listed.

Individual OBE2109 treatment group versus placebo comparisons will be made for superiority with an overall two-sided Type I error (alpha) of 0.05. In order to account for multiplicity given four different OBE2109 treatment groups, each primary endpoint comparison versus placebo will be conducted at the 0.0125 level of significance, i.e. 0.05 divided by 4. In addition, a sequential testing procedure within each OBE2109 treatment group will be used for the comparison of the following secondary endpoints versus placebo, where a formal statement of efficacy may be made, thus continuing to protect the overall type I error. An endpoint will only be claimed to be statistically significant if the resulting p-value for that endpoint and all endpoints higher up the testing order (for a given treatment arm) are less than 0.0125:

- 1. Reduced menstrual blood loss at 24 weeks of treatment (primary endpoint)
- 2. Time to reduced menstrual blood loss (i.e. \leq 80 mL and \geq 50% reduction from baseline) up to Week 24
- 3. Amenorrhea up to Week 24
- 4. Time to amenorrhea up to Week 24
- 5. Number of days of uterine bleeding for the 28-day interval up to Week 24
- 6. Hemoglobin level at Week 24

The additional efficacy endpoints will be tested at the 0.0125 with no further adjustments for multiplicity.

Unadjusted, ninety five percent (95%) confidence intervals will be presented throughout. Hypothesis testing (as described above) will be used to formally establish an effect, prior to returning to the estimation framework.

9.5.1. Baseline Assessment

Descriptive statistics will be performed on relevant screening and baseline data (i.e. data collected prior to the treatment administration) and on demographic characteristics. There will be no formal comparison of baseline data, that is, no statistical hypothesis testing.

The baseline value for the primary endpoint will be the mean of the menstrual blood loss assessed during the two, complete menstrual cycles at screening, which may not be exactly 28 days each. In the case that screening lasts three full cycles, the baseline will be calculated on the second and third cycles, i.e. those assessed for inclusion.

9.5.2. Primary Efficacy Analysis

The primary analysis set for the efficacy analyses will be the Full Analysis Set.

The primary analyses of reduced menstrual blood loss at 24 weeks of treatment (last 28 days prior to week 24 visit) will be analysed as a categorical variable (yes / no response) and will be conducted as follows:

Cochran-Mantel-Haenszel (CMH) tests with adjustment for the stratification factor race will be used to test the null hypothesis of no treatment effect for each OBE2109 group vs. placebo with regards to the

proportion of subjects with a reduced menstrual blood loss at 24 weeks. The odds ratios will be estimated from the CMH test together with the associated 95% CI and corresponding p-values. The proportion per treatment arm will be displayed together with exact Clopper-Pearson 95% CIs. The differences in percentages with corresponding 95% Newcombe-Wilson confidence intervals will also be presented. The homogeneity of the odds ratios will be explored using the Breslow-Day test.

In addition to the CMH tests and to further explore a possible interaction between race and treatment, a logistic regression model with terms for treatment, stratification factor race and the interaction between treatment and race will be fitted to the binary response data. Contrast and estimate statements will provide separated tests for each OBE2109 group vs. placebo for each strata. In case of too many empty cells or non-convergence of the model, separated Fisher's exact tests will be used for each comparison versus placebo, within strata. Subjects who discontinue prematurely due to lack of efficacy or adverse events, or who undergo operative or radiological interventions for uterine fibroids, will be considered as non-responders.

In order to account for multiplicity given four different OBE2109 treatment groups, each primary endpoint comparison versus placebo will be conducted at the 0.0125 level of significance, i.e. 0.05 divided by 4.

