In general, between group comparisons for continuous endpoints will be analyzed via repeated measures analysis of covariance, including the baseline and stratification factor race as a covariate, with each treatment group compared versus placebo using contrasts.

Mean hemoglobin will be compared between treatment groups and categorical analyses may also be performed.

Fibroid volume and uterine volume are expected to be log-normally distributed and so will be logtransformed prior to analysis, with the subsequent results (mean differences and corresponding confidence intervals) back transformed and hence reported in terms of ratios. The underlying distributions will be checked, and if deemed necessary alternative analyses may also be conducted. The number of days of uterine bleeding (assessed via the alkaline hematin method) will be analyzed using a negative binomial model or zero-inflated negative binomial, depending on model fit. The PGI-I will be analysed using Mantel-Haenszel methodology.

In order to explore the impact of submucosal fibroids on the efficacy of OBE2109, an analysis of the primary efficacy endpoint will be performed on the subset of patients from the FAS analysis set with a baseline FIGO classification of 0, 1 or 2 in either one fibroid only or in any fibroid, depending on the number of available fibroid data.

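### The primary test is valid, but neither it nor its supporting model uses baseline menstrual blood loss; adding it is a low-cost, optional gain in precision

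*Protocol*

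**What the plan says.** Protocol 3.1.1 defines response as a loss of at most 80 mL together with a reduction of at least 50% from baseline, over the last 28 days before the Week 24 visit. Section 9.5.2 sets the test: "Cochran-Mantel-Haenszel (CMH) tests with adjustment for the stratification factor race will be used". The same section adds a "logistic regression model with terms for treatment, stratification factor race and the interaction between" those two factors, with no baseline term.

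Section 9.5.1 takes the baseline from the screening period: "The baseline value for the primary endpoint will be the mean of the menstrual blood loss assessed during the two, complete menstrual cycles". For continuous endpoints, 9.5.3 plans a repeated measures model "including the baseline and stratification factor race as a covariate".

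On size, 9.2 works "under the assumption of a 30% response rate in placebo and 70% response rate in an active arm" and gives 64 per arm as the number "required for at least 90% power for rejecting all of the OBE2109 group vs placebo group comparisons". Section 5.1.2 plans 100 per arm, a total that 9.2 attributes mainly to exposure requirements for registration. Section 9.5 sets an "overall two-sided Type I error (alpha) of 0.05", which is split equally over the four active arms to give 0.0125 for each test.

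**The concern.** Response requires an on-treatment loss no greater than the smaller of 80 mL and half the baseline. The two limits meet at 160 mL. Up to that point every woman needs a 50% reduction. Above it the required reduction is 1 − 80/baseline, which is 60% at 200 mL and 73% at 300 mL. Unless drug effect or natural variation happens to offset this, women with heavier baseline bleeding should respond less often in every arm.

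A covariate that is prognostic, defined for the primary endpoint and already collected can reduce the variance of the treatment comparison. It also corrects chance imbalance in baseline loss between arms. The protocol adjusts for baseline in its continuous endpoints but in no primary-endpoint analysis that it describes. What is at stake is precision, and some power if an arm responds well below the planning rate. By 9.5, a failed primary test also closes the five ordered secondary endpoints for that arm.

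**Working it through.** **1. The plan's own figure.** Inputs from 9.2 and 9.5: p0 = 0.30, p1 = 0.70, two-sided 0.0125 per comparison (z = 2.498). Splitting the 10% type II error over four comparisons gives 97.5% power for each (z = 1.960).

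- n = [2.498·√(2·0.5·0.5) + 1.960·√(0.21 + 0.21)]² / 0.4² = 57.6, so 58.
- With continuity correction: (57.6/4)·[1 + √(1 + 4/(57.6·0.4))]² = 62.5, so 63.

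The stated 64 is reproduced to within one subject.

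**2. Power of the planned test at 100 per arm** (normal approximation, unadjusted): power = Φ{[d·√n − 2.498·√(2·p̄·q̄)] / √(p0q0 + p1q1)}.

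| Active response (placebo 30%) | Calculation | Power |
|---|---|---|
| 70% (protocol) | (4 − 1.766)/0.648 = 3.447 | 99.97% |
| 66.7% | (3.667 − 1.765)/0.657 = 2.892 | 99.8% |
| 55% (assumed) | (2.5 − 1.746)/0.676 = 1.115 | 86.7% |
| 50% (assumed) | (2 − 1.730)/0.678 = 0.397 | 65.4% |

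Joint power for all four comparisons at 70%, simulated with a shared placebo arm, is 99.87%. Under the protocol's assumptions, adjustment can therefore add at most 0.03 points per comparison and 0.13 points jointly.

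**3. Is baseline prognostic?** The protocol gives no distribution of baseline loss, so ranges were assumed: median true loss 150 to 200 mL, between-subject log-SD 0.5 to 0.6, within-subject log-SD 0.3 to 0.5, log-SD of the on-treatment ratio 0.8, and both screening cycles above 80 mL. The model includes regression to the mean. Response rates by baseline quartile, lowest to highest:

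| Setting | Placebo (30% overall) | Active (70% overall) |
|---|---|---|
| Weakest gradient (150 mL, 0.5, 0.5) | 0.35, 0.37, 0.29, 0.18 | 0.76, 0.78, 0.70, 0.56 |
| Strongest gradient (200 mL, 0.6, 0.3) | 0.45, 0.39, 0.25, 0.11 | 0.85, 0.81, 0.69, 0.46 |

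**4. What that is worth in precision.** With equal arms, standardizing over baseline lowers the variance of the risk difference by the fraction Var(m0 + m1) / [2(σ0² + σ1²)]. Here m0 and m1 are the response rates by baseline, and σ² is the overall binomial variance in each arm.

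- Weakest: 0.0256/0.838 = 3%.
- Strongest: 0.0796/0.838 = 9.5%.

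Simulation over a wider set of assumptions gives about 0 to 14%. That set includes active responses that come from complete suppression unrelated to baseline. At 30% versus 70%, the unadjusted 95% half-width is 1.96·√(0.42/100) = 12.7 points. A 14% fall in variance brings it to 12.7·√0.86 = 11.8 points.

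**5. What that is worth in power if an arm reached only 50%.** Multiplying both standard-deviation terms in step 2 by √(1 − reduction), and carrying the step 4 fractions over as an approximation:

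- 3%: (2 − 1.704)/0.668 = 0.443, power 67.1%, a gain of about 2 points.
- 9.5%: (2 − 1.646)/0.645 = 0.548, power 70.8%, a gain of about 5 points.

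Simulations agree on the order of size:

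- Baseline lognormal, median 190 mL, log-SD 0.5, truncated at 80 mL; ratio SD 0.6 to 1.3. Race-only CMH 65–68%, logistic with race and log baseline 69–71%. At 55% response, 86–87% against 89–91%. Null rejection is about 0.012 for both.
- Regression to the mean plus a suppressed fraction unrelated to baseline. At 50%, 65–67% against 66–67%. At 55%, 86–87% against 86–88%.
- Both features together over a range of assumed distributions: gains of about 1 to 7 points at 50%, never negative.

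Larger gains (65% rising to 76% or 83%) need a baseline effect of 1.0 or 1.5 log-odds per SD. The quartile rates in step 3 imply only about 0.35 to 0.75. This divides the top-to-bottom logit difference by 2.54, the distance in SD between the means of the outer quartiles of a normal variable.

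**The case against.** The strongest reply in favour of the plan is that nothing here is stated wrongly. CMH adjusted for the only randomization factor is a standard, valid test. Chance baseline imbalance is already covered by its error rate. Baseline adjustment in a repeated measures model does not oblige a binary endpoint to follow suit, so 9.5.2 and 9.5.3 are not inconsistent. All of this stands.

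A reader might infer that the plan gives away power at no cost, and might point to the Phase 2 fibroid subgroup in 1.5.2 (8 of 12 suppressed at 100 mg, 13 of 13 at 200 mg) as a sign that some arms will fall short. The documents do not support this. Eight of 12 is 67%, at which power is still 99.8%. That result also concerns suppression of menstruation in endometriosis patients, not the present endpoint. No active response rate near 50% appears in the protocol. Nor is adjustment free of cost, because the estimate becomes model-based.

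It can also be said that the size of any gain depends on unstated baseline distributions, and that it nearly vanishes if active responses are mostly complete suppression. This is correct, and it is why the range starts at zero. A logistic odds ratio adjusted for baseline would also differ in meaning from the race-stratified one. A standardized difference in proportions avoids that and matches the differences in percentages already planned in 9.5.2.

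A supportive baseline-adjusted analysis could sit in the unseen SAP. The primary test and the terms of the supporting model, however, are fixed in the protocol itself, so a suggestion about them is in order.

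**Conclusion.** The point holds as an optional efficiency improvement of low priority, not as an error. Both the primary test and its supporting logistic model omit a baseline value that is already collected and that the 80 mL limit makes plausibly prognostic above 160 mL. Under the protocol's own assumptions there is essentially no power to recover. The benefit is roughly 0 to 14% lower variance of the risk difference, at most about one percentage point off each side of the confidence interval. Power gains of about 1 to 7 points arise only if an arm's true response is near 50%. These ranges rest on assumed distributions of baseline loss and of on-treatment change, none of which the protocol gives. Type I error is not in question under either approach.

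**What to change.** Before the Week 24 unblinding, prespecify a logistic model with treatment, race and log baseline menstrual blood loss. Report from it a standardized (marginal) difference in proportions with its confidence interval for each active arm against placebo. Keep the race-stratified CMH test alongside it, and state in advance which of the two carries the 0.0125 test. If the sponsor prefers to leave the primary test untouched, the minimum change is to add baseline loss to the logistic model already planned in 9.5.2.

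Stratifying the CMH test by race and by baseline above or below 160 mL is not worth adopting. In the 190 mL simulation it gave 68% at 50% response and 87–89% at 55%, against 65–68% and 86–87% for race alone.

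The cost is a wording change and a few lines of code, with no new data. The downside is that the adjusted estimate depends on a model, which is the reason to keep the CMH result beside it.

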9.5.3. Secondary Efficacy Analysis

The endpoints amenorrhea, time to amenorrhea, menstrual blood loss and time to reduced menstrual blood loss will be assessed using data up to Week 24 and again using all data up to Week 52. For the subjects on the placebo arm who were randomized to switch treatment to OBE2019 at Week 24, only data up to the time they switch treatment will be used.

The analysis of amenorrhea will be conducted using the same methods as for the primary endpoint.

A sequential testing procedure will be used within each treatment group. Amenorrhea up to Week 24 vs. placebo will be tested at the 0.0125 significance level only if the primary endpoint hypothesis test is rejected, and in the same way, time to amenorrhea up to Week 24 will only be tested (at 0.0125) if the amenorrhea hypothesis test is rejected (see also the ordering of the sequential testing procedure described in section 9.5). The additional efficacy endpoints will be tested at the 0.0125 with no further adjustments for multiplicity.

Time to amenorrhea is defined as the number of days from first dose to the first day for which the subject does not have bleeding (see Section 6.3.1.2) for at least 35 days. Time to amenorrhea will be analyzed using Kaplan-Meier methodology (estimates and plots will be produced) and each OBE2109 group vs. placebo will be compared using a two-sided log-rank test stratified by race. In addition, the treatment difference as measured by the Hazard Ratio and its corresponding 95% Confidence Interval will be estimated using a stratified Cox regression model with race as stratification factor. Time to reduced menstrual blood loss (as defined by the primary endpoint) will be analysed in the same way.

For the 24-Week analysis, subjects who do not have any amenorrhea within the 24-Week period from Study Day 1 up to Week 24 visit will be considered as right-censored data. The date of the last alkaline hematin method assessment reported from Study Day 1 up to the Week 24 visit will be used as time of censoring. Data from the "last alkaline hematin method assessment" form of external data will be used. If no alkaline hematin method assessment is performed after Study Day 1, the date of Study Day 1 will be used as time of censoring.

In general, between group comparisons for continuous endpoints will be analyzed via repeated measures analysis of covariance, including the baseline and stratification factor race as a covariate, with each treatment group compared versus placebo using contrasts.

Mean hemoglobin will be compared between treatment groups and categorical analyses may also be performed.

Fibroid volume and uterine volume are expected to be log-normally distributed and so will be logtransformed prior to analysis, with the subsequent results (mean differences and corresponding confidence intervals) back transformed and hence reported in terms of ratios. The underlying distributions will be checked, and if deemed necessary alternative analyses may also be conducted. The number of days of uterine bleeding (assessed via the alkaline hematin method) will be analyzed using a negative binomial model or zero-inflated negative binomial, depending on model fit. The PGI-I will be analysed using Mantel-Haenszel methodology.

In order to explore the impact of submucosal fibroids on the efficacy of OBE2109, an analysis of the primary efficacy endpoint will be performed on the subset of patients from the FAS analysis set with a baseline FIGO classification of 0, 1 or 2 in either one fibroid only or in any fibroid, depending on the number of available fibroid data.

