1.5.2. Efficacy

In a Phase 2 clinical study in patients with endometriosis (Study KLH1202), 50, 100, or 200 mg OBE2109 or placebo was orally administered once daily after breakfast for 12 weeks. Approximately half of the 107 subjects presented with uterine fibroids as detailed in the table below. Post-hoc analyses were performed on this subgroup of subjects.

Treatment group	50 mg	100 mg	200 mg	Placebo
Ν	29	26	28	24
With Uterine Fibroids (N)	12	12	13	14
Fibroids diameter \geq 30mm (N)	4	4	7	5

The bleeding profile of the uterine fibroid subgroup was assessed and compared to the same data in the entire study population to establish the right dose for further clinical studies in uterine fibroid subjects. The 50 mg dose of OBE2109 suppressed the menstrual bleeding insufficiently in the full subject population and even less in the fibroid subgroup, as bleeding suppression was achieved in only 1 of 12 subjects of the 50 mg dose in the uterine fibroid subgroup. In the subgroup of uterine fibroid subjects,

the 100 mg and the 200 mg dose suppressed menstruation in 8 of 12 and in all 13 subjects, respectively. Similarly, assessment of the proportion of bleeding days indicated that for uterine fibroid subjects and especially for fibroid subjects with bigger fibroids (\geq 30mm of diameter) higher doses of OBE2109 are needed to control the menstrual bleeding. Consequently, it was decided that the 50 mg dose insufficiently controls uterine bleeding, and that for subjects with heavy menstrual bleeding due to fibroids the lowest dose to be tested should be the 100 mg dose.

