4. STUDY DESIGN

The study is a prospective, randomized, parallel group, double-blind, placebo-controlled phase 3 study investigating the efficacy and safety of OBE2109 alone and in combination with add-back therapy for the management of heavy menstrual bleeding associated with uterine fibroids in premenopausal women.

The study duration will be approximately 85 weeks per subject. If a washout is required for OC pill or other non-depot sex hormones, an additional period of up to 6 weeks is allowed between signing the informed consent and Screening. A schematic of the study design is shown in Figure 1.

The study starts with a screening period which must include at least two complete menstrual cycles but could include a third menstrual cycle if the menstrual blood loss volume measured by the Alkaline Hematin Method for the first eight days of the first menstrual period is \leq 80mL due to missed collection of sanitary protection. Screening will therefore last between 6 and up to a maximum of 17 weeks, excluding washout. During this period, the subject will receive no study drug.

Once the screening central lab and menstrual blood loss volume measured by Alkaline Hematin Method are received, all inclusion and exclusion criteria will be reviewed. If the eligibility is confirmed, the site will contact the subject to confirm her willingness to continue in the study. If the subject confirms, she will be randomized in a 1:1:1:1:1 ratio to one of five treatment groups:

- 1. Placebo OBE2109 + Placebo E2/NETA
- 2. OBE2109 100 mg + Placebo E2/NETA
- 3. OBE2109 100 mg + E2 1 mg/NETA 0.5 mg
- 4. OBE2109 200 mg + Placebo E2/NETA
- 5. OBE2109 200 mg + E2 1 mg/NETA 0.5 mg

An Interactive Web Response System (IWRS) will be used to allocate the appropriate treatment. In order to maintain the blind, all subjects not receiving add-back therapy will receive a matching placebo.

At Week 24 visit, half of the subjects from the Placebo OBE2109 + Placebo E2/NETA arm will be switched to OBE2109 200 mg with add-back (E2 1 mg/NETA 0.5 mg) group while the other half will remain on placebo. This allocation will be determined as part of the randomization and treatment will be continued up to Week 52.

From the Week 24 visit, all subjects in the OBE2109 200 mg without add-back group will receive add-back.

All subjects will be followed up for 24 weeks after end of treatment.

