6.3.1.2. Amenorrhea

Amenorrhea will be determined using the alkaline hematin method and is defined as having no sanitary material returned or volume < lower limit of quantification within at least a 35-day interval. Amenorrhea will be assessed using data up to Week 24, i.e. at least a 35-day interval up to Week 24 and again using all data up to Week 52.

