9.5.5. Missing Data

In order to take into account all randomized subjects in the analysis, the assessment of the primary endpoint for subjects who do not have menstrual bleeding data up to Week 24 (and who did not discontinue prematurely due to lack of efficacy or adverse events, or undergo operative or radiological interventions for uterine fibroids) will be based on the results from the last 28 days prior to the last diary completion. Subjects who have less than 28 days of data will be treated as non-responders. The secondary endpoint of amenorrhea will be assessed in a similar way.

Missing values for continuous efficacy endpoints analyzed via likelihood methods (e.g. repeated measures mixed models) will not be directly imputed as they are handled within the analysis itself, under the assumption that the model specification is correct and that the data is missing at random.

Sensitivity analyses will be conducted to check the robustness of the analysis results under alternative assumptions with regards to missing data. Further details on the handling of missing values and planned sensitivity analyses will be defined in the SAP.

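### Read literally, binary amenorrhea up to Week 52 carries forward any 35-day interval since Day 1 and gives half of the placebo arm only 24 weeks to qualify

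*Protocol*

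**What the plan says.** Section 3.1.2 lists amenorrhea up to Weeks 24 and 52 as a secondary endpoint. Section 6.3.1.2 describes it as "defined as having no sanitary material returned or volume < lower limit of quantification within at least a 35-day interval", assessed over "at least a 35-day interval up to Week 24 and again using all data up to Week 52". Section 9.5.3 repeats the window: the endpoint "will be assessed using data up to Week 24 and again using all data up to Week 52". The same section analyses binary amenorrhea with the methods of the primary endpoint, which in 9.5.2 means CMH tests adjusted for race. For placebo women randomised to switch at Week 24, it uses only data up to the switch.

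Two other statements bear on the window, and they point in different directions.
- For the time-to-event version, 9.5.3 censors "subjects who do not have any amenorrhea within the 24-Week period from Study Day 1 up to Week 24 visit". That is the language of an endpoint met at any time.
- Section 9.5.5 bases the primary endpoint, for women without data to Week 24, on the final 28 days ending at the last diary entry. It then adds: "The secondary endpoint of amenorrhea will be assessed in a similar way". That is the language of a status at the end of the period.

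**The concern.** An endpoint labelled Week 52 will usually be read as describing women at about Week 52. If it counts any qualifying interval since Day 1, it mainly carries the Week 24 successes forward and adds late first successes. Apart from reclassified women, the proportion can only stay level or rise.

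The comparison with placebo has a second problem. Active-arm women can qualify at any time over 52 weeks, while half of the placebo arm stops contributing at Week 24. A binary CMH test does not adjust for unequal time at risk, so active arms gain an advantage that is not a treatment effect. At stake are the size of the reported Week 52 amenorrhea rate and the fairness of its contrast with placebo.

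**Working it through.** **Figures in the protocol.** It gives no amenorrhea rate and no calculation for a Week 52 endpoint. The sample size in 9.2 concerns the primary endpoint and does not bear on this point. The nearest clinical figure is in 1.5.2: "the 100 mg and the 200 mg dose suppressed menstruation in 8 of 12 and in all 13 subjects, respectively". It comes from a 12-week post-hoc subgroup of an endometriosis study, with no stated 35-day alkaline hematin criterion, so it is not used as an input. All rates below are assumed.

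**Step 1: carry-over.** Let *e* be the share qualifying by Week 24, *n* the share of the remainder who first qualify in Weeks 24 to 52, and *r* the share of early responders whose bleeding returns. Leavers are set aside, and new responders are assumed still amenorrheic at Week 52.

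- Ever met by Week 52 = e + (1 − e)n
- Amenorrheic late in the period = e(1 − r) + (1 − e)n

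| e | n | r | Ever met | Late status |
|---|---|---|---|---|
| 0.50 | 0.10 | 0 | 0.50 + 0.05 = 55% | 55% |
| 0.50 | 0.10 | 0.20 | 55% | 0.40 + 0.05 = 45% |
| 0.50 | 0.10 | 0.50 | 55% | 0.25 + 0.05 = 30% |
| 0.70 | 0.10 | 0.50 | 0.70 + 0.03 = 73% | 0.35 + 0.03 = 38% |

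The ever-met rate does not depend on *r*.

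**Step 2: unequal time to qualify.** Week 24 is 168 days and Week 52 is 364 days. Give active and placebo women the same constant hazard, so that there is no true effect, and let *p* be the share qualifying by Week 24.

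- Active by Week 52 = 1 − (1 − p)^(364/168)
- Placebo = 0.5 × p + 0.5 × [1 − (1 − p)^(364/168)]

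For p = 0.10, active is 1 − 0.90^2.167 = 0.204. Placebo is 0.5 × 0.10 + 0.5 × 0.204 = 0.152.

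| Assumed p | Active, 52 weeks | Placebo, half cut at Week 24 | Approximate chance of p < 0.0125, 100 per arm |
|---|---|---|---|
| 0.05 | 10.5% | 7.8% | 3.4% |
| 0.10 | 20.4% | 15.2% | 6.2% |
| 0.20 | 38.3% | 29.2% | 12.9% |

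The last column is an unstratified two-proportion approximation. With no true effect it should be about 1.25%.

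**Step 3: which reading the text supports.** Sections 6.3.1.2 and 9.5.3 both refer to all data and set no end-of-period anchor. The primary endpoint, by contrast, is tied explicitly to the 28 days before its visit. This favours the ever-met reading. The sentence in 9.5.5 favours end-of-period status, but it sits in the missing-data section and concerns women who lack data. The text leans to ever met without settling it.

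**The case against.** The case on the other side is substantial, and much of it stands.

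- **The window is not certain.** An interval up to a visit can mean one that ends there, and 9.5.5 leans that way. This stands, and it is why the sections must be reconciled.
- **The rate can fall.** If the rules in 9.5.2 carry over with the methods, a woman who discontinues for lack of efficacy or an adverse event, or who has a fibroid intervention, becomes a non-responder despite earlier amenorrhea. This stands. The carry-over applies to women not reclassified in this way.
- **First-event times are legitimate.** A reader might infer that the Week 52 times to amenorrhea and to reduced blood loss are also faulty. They are not. Time to amenorrhea is the "number of days from first dose to the first day for which the subject does not have bleeding" for at least 35 days, so keeping early events is what such an endpoint does. Kaplan-Meier and log-rank methods handle the shorter placebo follow-up by censoring.
- **Persistence is measured elsewhere.** A reader might infer that the trial cannot show whether its effect lasts. Sections 3.1.2 and 3.1.3 list bleeding days, blood loss volume and reduced blood loss for each 28-day interval up to Week 52. None of these is 35-day amenorrhea, but they do show returning bleeding.
- **The regimen change is disclosed.** Section 4 states: "From the Week 24 visit, all subjects in the OBE2109 200 mg without add-back group will receive add-back". A reader might infer that Week 52 results will be credited to 200 mg alone. No section says so. How that arm is named in Week 52 tables is a reporting matter.

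**Conclusion.** The point holds for binary amenorrhea up to Week 52 and nothing wider. On the literal wording, its rate keeps earlier successes whatever happens later, leavers aside. Its CMH comparison also favours active arms because half of placebo is cut at Week 24. On assumed rates, the ever-met figure stays at 55% while late status falls from 55% to 30% as relapse among early responders rises from 0 to 50%. Unequal follow-up alone produces about 20% against 15% when 10% qualify by Week 24, and between 10.5% against 7.8% and 38.3% against 29.2% over the range shown. These sizes rest on assumed rates and, for the second, on a common constant hazard. Both also assume the ever-met reading, which 9.5.5 leaves in some doubt.

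A reader might go further and infer that a confirmatory claim or the overall type I error is at risk. The documents do not support that: the hierarchy in 9.5 has six steps, all at Week 24. This is a worthwhile, inexpensive correction to one Week 52 estimate and its placebo comparison.

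**What to change.** In 6.3.1.2 and 9.5.3, define Week 52 amenorrhea as no measurable blood loss for at least the last 35 days before the Week 52 visit. Compare each active arm with the women randomised to stay on placebo. That half is fixed at initial randomisation (9.3), so the comparison remains randomised. Report the cumulative version, any 35-day interval since Day 1, as descriptive only. Reword the amenorrhea sentence in 9.5.5 to agree with these definitions, and say whether the non-responder rules of 9.5.2 apply to the Week 52 endpoint. Leave the Week 24 definition and the time-to-event endpoints unchanged.

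This removes both the carry-over and the unequal follow-up, using alkaline hematin data already collected to Week 52. The cost is a few sentences, a Week 52 percentage that will be equal or lower, and a placebo comparator of about 50 instead of about 100 women. With 100 active women and equal variances, the standard error of the difference grows by √[(1/100 + 1/50)/(1/100 + 1/100)] = √1.5 ≈ 1.22, or about 22%.
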